16. ADVERSE EVENTS AND DEVICE DEFICIENCIES

16.1 DEFINITIONS

The categories of adverse events are shown in Table 4. The definitions for each of these categories are given in the subsequent sections (see reference within the table). All adverse events will be captured from the time of surgery through the 12-month follow-up visit.

[Intentionally left blank]

CONFIDENTIAL AND PROPRIETARY

This document contains information that is confidential and proprietary to Smith & Nephew PLC and Smith & Nephew, Inc. and is intended for use only by Smith & Nephew and its manufacturer. It shall not be reproduced or copied in whole or in part, nor shall the contents be disclosed by any means without prior written permission from Smith & Nephew, nor shall anyone make any use of it that is contrary to the expressed or implied wishes of Smith & Nephew.

Study Protocol—Device	
PMCF Study on PEEK Suture Anchors for Hip Indications	Number: 2018.14.SMD.PEEK.RET.HIP
	Version: 2.0, 03 April 2019
	Page: 44 of 63

Table 5: Categories of Adverse Events

		DEVICE- OR PROCEDURE-RELATED	
		NOT DEVICE-RELATED	
NON-SERIOUS	ADVERSE EVENT (AE)	ADVERSE DEVICE EFFECT (ADE)	
SERIOUS	SERIOUS ADVERSE EVENT (SAE)	SERIOUS ADVERSE DEVICE EFFECT (SADE)	
		ANTICIPATED	UNANTICIPATED
		ANTICIPATED SERIOUS ADVERSE DEVICE EFFECT (ASADE)	UNANTICIPATED SERIOUS ADVERSE DEVICE EFFECT (USADE)

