	Bioraptor Knotless Suture Anchor	20 subjects per site	40 subjects per site	120 subjects
	SpeedLock Hip	20 subjects per site	40 subjects per site	120 subjects
	Total	40 subjects	80 subjects	240 subjects
Number of Study Sites:	Up to 6 sites			
Targeted Global Regions:	USA			
Inclusion Criteria:	
 1. Subjects who have undergone hip joint repair using the study devices. 2. Subjects aged 18 years and older at the time of surgery. 3. Subjects must have had a visit to their provider between 6 and 15 months post-operative. 			
Exclusion Criteria:	
 1. Subjects who are < 12 months post-operative. 2. Subject is entered in another investigational drug, biologic, or device study or has been treated with an investigational product within 30 days prior to surgery. 3. Subject had off-label use of the PEEK suture anchor during surgery. 			
Study Duration:	Twelve month follow-up			
Primary Endpoint:	Clinical success rate (%) at 6 months post-operative based on standard of care			
Secondary Endpoint:	Clinical success rate (%) at 12 months post-operative based on standard of care			
Exploratory Outcomes:	Surgeon Reported Outcomes based on data collected on the subject's medical chart as standard of care at study sites. These may include but not restricted to the following:			

CONFIDENTIAL AND PROPRIETARY

This document contains information that is confidential and proprietary to Smith & Nephew PLC and Smith & Nephew, Inc. and is intended for use only by Smith & Nephew and its manufacturer. It shall not be reproduced or copied in whole or in part, nor shall the contents be disclosed by any means without prior written permission from Smith & Nephew, nor shall anyone make any use of it that is contrary to the expressed or implied wishes of Smith & Nephew.

Study Protocol—Device	
PMCF Study on PEEK Suture Anchors for Hip Indications	Number: 2018.14.SMD.PEEK.RET.HIP
	Version: 2.0, 03 April 2019
	Page: 22 of 63

	
 • Range of Motion (ROM) 
 • Flexion • Extension • Abduction • Adduction • External/Internal Rotation • Pain assessed by VAS
Safety Endpoints:	
 • All AEs, SAEs and complications including intra-operative adverse events and complications. • Device related intervention • Device deficiency

CONFIDENTIAL AND PROPRIETARY

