5. SCHEDULE OF EVENTS

Table 1: Schedule of Events

Schedule of Events	Chart Review	
	182 days post-op 6M (\pm 91 Days)	365 days post-op 12M (\pm 91 Days)
Informed Consent	X NA if waiver of consent granted by IRB	
Inclusion/Exclusion	X	
Demographics/Medical History	X	
VAS, ROM	X	X
Operative Data Collection	X	
Implant Status and / or Disposition	X	X
Concomitant Medications or Therapies ¹	X	X
AE, SAE and DevD Assessment	X	X
End of Study		X ²

¹ Any concomitant medications associated with an AE, SA(D)E will be recorded.

² End of Study CRF can be completed at 6 months if the subject did not have a 12-month visit.

CONFIDENTIAL AND PROPRIETARY

This document contains information that is confidential and proprietary to Smith & Nephew PLC and Smith & Nephew, Inc. and is intended for use only by Smith & Nephew and its manufacturer. It shall not be reproduced or copied in whole or in part, nor shall the contents be disclosed by any means without prior written permission from Smith & Nephew, nor shall anyone make any use of it that is contrary to the expressed or implied wishes of Smith & Nephew.

Study Protocol—Device	
PMCF Study on PEEK Suture Anchors for Hip Indications	Number: 2018.14.SMD.PEEK.RET.HIP
	Version: 2.0, 03 April 2019
	Page: 24 of 63

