11.3 EXCLUSION CRITERIA

Any one (1) of the following criteria will disqualify a potential subject from participation in the study:

1. Subjects who are < 12 months post-operative.
2. Subject is entered in another investigational drug, biologic, or device study or has been treated with an investigational product within 30 days prior to surgery.
3. Subject had off-label use of the PEEK suture anchor during surgery.

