1. VAS, ROM
2. Implant Status/Disposition
3. Document concomitant medications and/or therapies associated with an AE, SA(D)E
4. Review the subject's chart for AEs, SAEs and Device Deficiencies including inter-operative. AEs, SAEs and DevDs should be documented from the time of surgery through the study duration.
5. Complete the End of Study CRF.

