13.3 CONCOMITANT MEDICATIONS AND THERAPIES

Any concomitant medications associated with an AE, SAE or SADE will be recorded. Concomitant medications will be recorded from the time of surgery through 12 months. If the subject's final visit occurred at 6 months, concomitant medications will be collected through 6 months.

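### The plan gives conflicting end points for event capture; under section 16.1 it ends at a visit that may fall anywhere from day 274 to day 456, so adverse event percentages rest on unequal exposure

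*Combined protocol and SAP*

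**What the plan says.** Several places in the protocol set the end of event capture, and they differ.

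- **Section 16.1:** "All adverse events will be captured from the time of surgery through the 12-month follow-up visit". The end is a visit, not a day.
- **Section 5, Table 1:** the 12-month review is at 365 days ± 91 days and the 6-month review at 182 days ± 91 days. Footnote 2 adds: "End of Study CRF can be completed at 6 months if the subject did not have a 12-month visit".
- **Sections 13.1 and 13.2** (the chart-review steps): "AEs, SAEs and DevDs should be documented from the time of surgery through the study duration". The synopsis gives the duration as "Twelve month follow-up".
- **Section 12.3.3:** safety endpoints run from enrollment to termination or completion of the study, and include intra-operative events.
- **Section 13.3:** "If the subject's final visit occurred at 6 months, concomitant medications will be collected through 6 months". This concerns medications only.
- **Section 14.5:** device-related failure and re-intervention are counted if they occur on study; no day is given.

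Two eligibility rules bear on this. Exclusion 1 in section 11.3 removes "Subjects who are < 12 months post-operative", so a full year has passed before any chart is reviewed. Inclusion 3 in section 11.2 asks for one visit between 3 and 15 months (the synopsis says 6 and 15), so a visit in the 12-month window is not required.

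**The concern.** A prospective study usually has to stop counting at the last visit. A chart review does not, because the first year is already over when the abstractor opens the record. Tying the end of capture to a visit therefore gives up information for no design reason, and gives each subject a different observation time.

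Sections 14.4 and 14.5 report crude frequencies and percentages. Those are readable as 12-month risks only if everyone was observed for the same period. With an end anywhere from day 274 to day 456, they are not.

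The conflict between sections adds a second problem. One site may follow section 16.1, another the steps in 13.1 and 13.2, and a third may treat the End of Study form as closing the subject. Capture could then differ by site. A charted event that was never abstracted cannot be recovered by any later analysis. The study is meant to supply post-market safety and performance evidence, so the event rates are a main product.

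**Working it through.** **Inputs.** Table 1: 365 ± 91 days and 182 ± 91 days. Section 16.1: capture ends at the 12-month visit. Section 11.3: at least 12 months since surgery. Section 15: planning success rate 91%, used below only for illustration.

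**1. Windows.**
- 12-month review: 365 − 91 = 274 to 365 + 91 = 456.
- 6-month review: 182 − 91 = 91 to 182 + 91 = 273.

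**2. First-year days not covered if capture ends on day d: 365 − d.**

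| Capture ends | Days of year 1 not covered | Share of 365 |
|---|---|---|
| Day 274 (earliest 12-month visit) | 91 | 24.9% |
| Day 365 | 0 | 0% |
| Day 456 (latest 12-month visit) | none; 91 extra days | – |
| Day 273 (latest 6-month review) | 92 | 25.2% |
| Day 182 (nominal 6-month review) | 183 | 50.1% |
| Day 91 (earliest 6-month review) | 274 | 75.1% |

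The first three rows follow from section 16.1 as written. The last three apply only if a 6-month close-out also ends event capture.

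**3. The windows side by side.**
- Section 16.1 and sections 13.1/13.2 agree only for a subject whose 12-month visit falls on day 365.
- Section 12.3.3 starts at enrollment, which exclusion 1 places at least 12 months after surgery. Taken literally, that start falls after the first post-operative year, although the same sentence includes intra-operative events.
- For a subject without a 12-month visit, section 16.1 names an end that never occurs.

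**4. Balance of early and late visits.** Assume, for illustration, that 12-month visits spread evenly over days 274 to 456. The mean end of capture is (274 + 456)/2 = 365. About half of subjects end early, losing 91/2 = 45.5 days on average, and about half end late, gaining 45.5 days on average. The mean exposure is one year, but the individual exposures are unequal.

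**5. Upper-bound illustration in events.** Assume a 12-month cumulative failure F, a constant hazard, all subjects stopping on the same day d, and failures captured under the same window. Share missed = F − [1 − (1 − F)^(d/365)].
- F = 9%, d = 274: 0.09 − (1 − 0.91^0.7507) = 0.0217, or 2.2 points; 120 × 0.0217 ≈ 2.6 failures per 120 subjects.
- F = 9%, d = 182: 0.09 − (1 − 0.91^0.4986) = 0.0441, or 4.4 points; 120 × 0.0441 ≈ 5.3 per 120.
- F from 3% to 20%: 0.7 to 4.6 points at day 274, and 1.5 to 9.5 points at day 182.

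The documents give neither the timing of events nor the share of subjects without a 12-month visit, so these are bounds under assumptions, not estimates.

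**The case against.** The strongest reply is that the working instructions to sites are sections 13.1 and 13.2, which run capture through the study duration, and the synopsis makes that twelve months. On that reading nothing in the first year is lost. The reading is legitimate, but it contradicts section 16.1, and nothing says which prevails. What stands is that an early stop is not settled; the defect is a set of unreconciled windows.

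Four stronger readings are tempting, and the documents do not support them.

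- **That adverse event capture stops at the 6-month review when there was no 12-month visit.** Footnote 2 is permissive and concerns one form, and section 13.3 limits only medications. No section ends adverse event capture there. A site could still reasonably infer it, since those medications are the ones tied to adverse events and the later event search is a step of the 12-month review.
- **That section 16.1 truncates device failures and so biases 12-month success upward.** Its sentence concerns adverse events. Failure and re-intervention are surgeon-assessed, implant status is a separate item at both reviews, and their cut-off is undefined rather than set at a visit.
- **That the missed events are certainly in the chart.** Exclusion 1 shows that time has elapsed, not that a later event reached the site's record.
- **That the effect can only favour the device.** For subjects ended before day 365 truncation can only remove events, but late visits add up to 91 days, so the net direction is not fixed.

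It is also fair to say that section 12.3.2 expects 12-month data to be consistently available, which would limit how many subjects are closed early. Finally, a day-274 stop does not touch the 6-month primary endpoint, and the study tests no hypothesis.

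**Conclusion.** The concern holds as a conflict between capture windows, with a visit-based end in section 16.1 that a retrospective study does not need. Under that section as written, observation among subjects with a 12-month visit ranges from 274 to 456 days. Up to 91 days (24.9%) of the first year are unabstracted at one end, and up to 91 days are added at the other. Adverse event percentages therefore rest on unequal exposure, and charted events before day 365 can be lost.

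A loss of 92 to 274 days depends on the further assumption that sites treat a 6-month close-out as the end of event capture. Device failure and re-intervention may be affected in the same way, because their window is not defined in days.

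Severity is moderate. The windows are exact arithmetic, but the number of events at stake is unknown. Even the upper bound with every subject stopped at day 274 is 2.2 points at an assumed 9% failure rate with constant hazard.

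**What to change.** Set one common window in sections 16.1, 12.3.3, 13.1, 13.2 and 13.3: for every subject, abstract all charted adverse events, serious adverse events, device deficiencies, device failures, re-interventions and associated medications from surgery through day 365, whether or not a 12-month visit took place.

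Amend footnote 2 of Table 1 so that the End of Study form is completed only after the chart has been searched to day 365, and a missing 12-month visit waives only the pain and range-of-motion assessments.

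Keep events after day 365 out of the 12-month estimates, even where a visit or the chart runs to day 456; otherwise unequal follow-up returns.

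Record the date of last chart contact for each subject. A chart with no later entry is not evidence of success, and such subjects should not be counted as confirmed 12-month successes.

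The cost is wording in five sections and one footnote, one extra date on the form, and a little more abstraction time in charts that are already open. No new subjects or procedures are needed. The reported rates may be slightly less favourable to the device.

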16.1.1 Adverse Event

An Adverse Event (AE) is any untoward medical occurrence temporally associated with the use of an IP/Ancillary Product, whether or not considered causally related to that IP/Ancillary Product.

AE is used both to refer to AE which are non-serious non-IP or procedure-related and as an umbrella term referring to adverse events of all classifications.

An AE can be any unfavorable and unintended sign (for example, an abnormal laboratory finding), symptom, or disease. For reporting purposes, emphasis is placed first and foremost on whether or not the event constitutes an untoward medical occurrence.

16.1.2 Adverse Device Effect

An Adverse Device Effect (ADE) is an adverse event that, in the opinion of the investigator, is related to the IP or the procedure.

CONFIDENTIAL AND PROPRIETARY

This document contains information that is confidential and proprietary to Smith & Nephew PLC and Smith & Nephew, Inc. and is intended for use only by Smith & Nephew and its manufacturer. It shall not be reproduced or copied in whole or in part, nor shall the contents be disclosed by any means without prior written permission from Smith & Nephew, nor shall anyone make any use of it that is contrary to the expressed or implied wishes of Smith & Nephew.

Study Protocol—Device	
PMCF Study on PEEK Suture Anchors for Hip Indications	Number: 2018.14.SMD.PEEK.RET.HIP
	Version: 2.0, 03 April 2019
	Page: 45 of 63

Not Related - An AE is considered to be not related to the use of an IP or the procedure when the effect is DEFINITELY UNRELATED or UNLIKELY to have any relationship to the use of the IP or the procedure.

Related – An AE is considered to be related to the use of an IP or the procedure when there is a POSSIBLE, PROBABLE, or DEFINITE relationship between the AE and the use of the IP or the procedure.

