14.4 SAFETY ANALYSES

- All safety endpoints will be summarized using the safety population. The incidence of events encountered on study will be summarized using frequencies and percentages. An overall AE table will be summarized using the overall incidence according to subjects with at least one AE; subjects with at least one AE by worst severity (mild, moderate, or severe); subjects with at least one AE by worst outcome; subjects with one AE that led to study discontinuation; subjects with at least one AE by relatedness to investigational device; SAEs; ADEs; ASADEs; USADEs and SADEs as applicable. A cumulative summary by the number of events encountered within each classification will also be summarized. The incidence of subjects reporting device deficiencies will additionally be summarized.
- Each of the AE classifications will further be summarized by event using the frequencies (n) and percentages (%) of subjects with each event as well as the cumulative events/episodes per event.
- A listing of concomitant medications will be provided by subject.

CONFIDENTIAL AND PROPRIETARY

This document contains information that is confidential and proprietary to Smith & Nephew PLC and Smith & Nephew, Inc. and is intended for use only by Smith & Nephew and its manufacturer. It shall not be reproduced or copied in whole or in part, nor shall the contents be disclosed by any means without prior written permission from Smith & Nephew, nor shall anyone make any use of it that is contrary to the expressed or implied wishes of Smith & Nephew.

Study Protocol—Device	
PMCF Study on PEEK Suture Anchors for Hip Indications	Number: 2018.14.SMD.PEEK.RET.HIP
	Version: 2.0, 03 April 2019
	Page: 42 of 63

Additional summaries of safety endpoints, if applicable, will be described in the SAP.

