16.1.3 Serious Adverse Events and Serious Adverse Device Effects

An AE or ADE is considered a **Serious** Adverse Event (SAE) or **Serious** Adverse Device Effects (SADE) if, in the view of either the Investigator or the Sponsor, it:

- Results in death.
- Is life-threatening (*NOTE:* The term “life-threatening” in the definition of “serious” refers to an event/reaction in which the subject was at risk of death at the time of the event/reaction; it does not refer to an event/ reaction which hypothetically might have caused death if it were more severe).
- Requires in subject hospitalization or results in prolongation of existing hospitalization.
- Results in persistent or significant incapacity or substantial disruption of the ability to conduct normal life functions.
- Is a congenital anomaly/birth defect.
- Is a medically important event or reaction.

Medical and scientific judgment should be exercised in deciding whether other situations should be considered serious such as important medical events that might not be immediately life

CONFIDENTIAL AND PROPRIETARY

This document contains information that is confidential and proprietary to Smith & Nephew PLC and Smith & Nephew, Inc. and is intended for use only by Smith & Nephew and its manufacturer. It shall not be reproduced or copied in whole or in part, nor shall the contents be disclosed by any means without prior written permission from Smith & Nephew, nor shall anyone make any use of it that is contrary to the expressed or implied wishes of Smith & Nephew.

Study Protocol—Device	
PMCF Study on PEEK Suture Anchors for Hip Indications	Number: 2018.14.SMD.PEEK.RET.HIP
	Version: 2.0, 03 April 2019
	Page: 46 of 63

threatening or result in death or hospitalization but might jeopardize the subject or might require intervention to prevent one of the other outcomes listed in the definition above. Examples of such events are intensive treatment in an emergency room or at home for allergic bronchospasm, blood dyscrasias, or convulsions that do not result in hospitalization, or development of drug dependency or drug abuse.

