16.1.4 Anticipated/Unanticipated Serious Adverse Device Effect

An Unanticipated Serious Adverse Device Effect (USADE) is a serious ADE that meets any of the above definitions but is also considered, by the Investigator, to be caused by or related to the IP, not previously identified in nature, severity or degree in the IFU.

An Anticipated Serious Adverse Device Effect (ASADE) is a serious ADE that does not meet the criteria for a USADE.

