16.2 REPORTING PROCEDURES

AE of any kind and DevD will be recorded in the applicable CRF and source notes. The Investigator will evaluate all AE for relationship to the device and procedure, if applicable, seriousness, and severity. ADE, SAE, and DevD will be entered into the CRF and reported to the Sponsor within 24 hours of the investigator being informed about the event (Figure 1). Applicable to the retrospective study design, 24 hour reporting begins at the time the Investigator was informed of the event under the auspice of the clinical study. For ADE and DevD, details of the product/procedure related to the event will be included and where applicable and available, pictures taken of the device. If available the deficient product should be retained for return to S&N unless it is contaminated (e.g. used dressings must not be retained).

All SAE and ADE will be reviewed by a medically qualified person appointed by the Sponsor to determine which, if any, meet criteria for expedited reporting to the regulatory authorities. The investigator will inform the IRB/IEC of adverse events according to the IRB/IEC requirements. Depending on the nature of the adverse event, S&N may request copies of the subject's medical records, imaging, operative notes, as well as results of any relevant laboratory tests performed or

[figure not shown]
CONFIDENTIAL AND PROPRIETARY

This document contains information that is confidential and proprietary to Smith & Nephew PLC and Smith & Nephew, Inc. and is intended for use only by Smith & Nephew and its manufacturer. It shall not be reproduced or copied in whole or in part, nor shall the contents be disclosed by any means without prior written permission from Smith & Nephew, nor shall anyone make any use of it that is contrary to the expressed or implied wishes of Smith & Nephew.

Study Protocol—Device	
PMCF Study on PEEK Suture Anchors for Hip Indications	Number: 2018.14.SMD.PEEK.RET.HIP
	Version: 2.0, 03 April 2019
	Page: 48 of 63

other documentation related to the AE. If the subject was hospitalized, a copy of the discharge summary may be requested by S&N and should be forwarded as soon as it becomes available. In certain cases, S&N also may request a letter from the Investigator that summarizes the events related to the case.

Figure 1: Evaluation and Reporting of AE and DevD

CONFIDENTIAL AND PROPRIETARY

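### Adverse device effects are defined to include events related only to the surgery, so the ADE, SADE and ASADE incidences are not device-only rates, and the device-relatedness row has no device-only definition behind it

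*Combined protocol and SAP*

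**What the plan says.** The relevant text is in sections 16.1 to 16.2 (definitions and reporting) and section 14.4 (safety analyses).

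- **ADE (16.1.2).** An ADE "is an adverse event that, in the opinion of the investigator, is related to the IP or the procedure".
- **Related (16.1.2).** "An AE is considered to be related to the use of an IP or the procedure when there is a POSSIBLE, PROBABLE, or DEFINITE relationship". The rule for not related uses the same joint wording. No grade for the device alone is defined.
- **Table 5 (16.1).** One of its headings reads "DEVICE- OR PROCEDURE-RELATED", which agrees with the text of 16.1.2.
- **Serious events (16.1.3).** "An AE or ADE is considered a Serious Adverse Event (SAE) or Serious Adverse Device Effects (SADE) if" it meets one of the listed seriousness criteria. A SADE is therefore an ADE that is serious.
- **Unanticipated (16.1.4).** A USADE is a serious ADE that the investigator also considers "to be caused by or related to the IP, not previously identified in nature, severity or degree in the IFU".
- **Anticipated (16.1.4).** An ASADE "is a serious ADE that does not meet the criteria for a USADE".
- **Assessment (16.2).** "The Investigator will evaluate all AE for relationship to the device and procedure, if applicable, seriousness, and severity". The sentence does not say whether device and procedure are recorded as separate items.
- **Analysis (14.4).** The overall table includes "subjects with at least one AE by relatedness to investigational device" and then counts SAEs, ADEs, ASADEs, USADEs and SADEs. It has no row for procedure-related events.

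**The concern.** The primary objective (section 9.1) is the safety and performance of the anchors. The study is a single-arm retrospective case series, and adverse events are captured from the time of surgery, intra-operative complications included. With no comparator, no background rate of surgical complications can be subtracted. The investigator's attribution is the only means of separating the anchor from the operation.

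The ADE definition merges the two. A reader of the clinical study report who sees an ADE or SADE percentage will naturally take it as a rate of harm attributed to the device, although it also contains events attributed only to the surgery. The row that could resolve this, relatedness to the investigational device, relies on a term that the protocol defines only for device and procedure together. Two analysts could fill that row differently and both be following the text.

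**Working it through.** The plan states no ADE rate, so there is no figure to reproduce. The check is to run each type of event through the definitions as written.

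| Related to device | Related to procedure | Serious | Identified in IFU | Class under 16.1.2 to 16.1.4 |
|---|---|---|---|---|
| yes | yes or no | no | either | ADE |
| no | yes | no | either | ADE |
| no | no | no | either | AE |
| no | no | yes | either | SAE |
| yes | yes or no | yes | no | SADE, USADE |
| yes | yes or no | yes | yes | SADE, ASADE |
| no | yes | yes | yes | SADE, ASADE |
| no | yes | yes | **no** | SADE, **ASADE** |

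Two results follow.

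1. Procedure-only events enter the ADE, SADE and ASADE counts. Only USADE excludes them, because it alone requires relation to the IP.
2. In the last line, a serious procedure-only event that the IFU does not identify fails the USADE test on the device requirement. ASADE is the remainder, so the event is labelled anticipated although nothing anticipated it.

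**Illustration of size.** All rates here are assumptions; none comes from the documents. Let *d* be the proportion of subjects with a device-related event and *p* the proportion with a procedure-only event, independent of each other. The ADE incidence as defined is

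ADE = 1 − (1 − d)(1 − p), and its ratio to the device-related incidence is ADE / d.

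| d | p | ADE as defined | Ratio to d |
|---|---|---|---|
| 1% | 5% | 1 − 0.99 × 0.95 = 5.95% | 5.95 |
| 1% | 15% | 1 − 0.99 × 0.85 = 15.85% | 15.85 |
| 2% | 10% | 1 − 0.98 × 0.90 = 11.8% | 5.9 |
| 3% | 5% | 1 − 0.97 × 0.95 = 7.85% | 2.6 |
| 3% | 15% | 1 − 0.97 × 0.85 = 17.55% | 5.85 |

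In the middle case, with the maximum of 120 subjects for one anchor, about 14 subjects would be counted with an ADE (0.118 × 120 = 14.2), against 2 to 3 with a device-related event (0.02 × 120 = 2.4).

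A limiting case is 240 subjects with no device-related event and 5% procedure-only. The ADE count is 12/240 = 5.0% (exact 95% CI 2.6% to 8.6%) and the device-related count is 0/240 (exact 95% CI 0% to 1.5%). The intervals are added here for scale; section 14.4 plans none for ADEs.

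**The case against.** The case on the other side has real substance.

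- **Other device results exist.** A reader might infer that the ADE and SADE rates are the study's device-safety results. The documents do not support that. Section 12.3.3 names device-related intervention and device deficiency as safety endpoints. Section 14.5 summarises device-related failure and device-related re-intervention, each with an exact CI. The primary endpoint is itself freedom from device failure and/or re-intervention. This stands, and it limits the reach of the point.
- **The plan already points to separation.** Section 16.2 names both device and procedure, and section 14.4 has a row that names the device only. The CRF is not among the documents, and it may hold two fields. This stands in part: the intention is visible, but the only written meaning of related is joint, and nothing says that the device row uses anything else.
- **A hidden device signal is not shown.** One might infer that a true device problem would be lost in the merged count. Section 14.4 also tabulates each classification by event, so anchor-specific events would appear by name. The documents support blurred attribution, not concealment.
- **Table 5.** One might read it as placing a procedure-only event in two columns at once. The table is broken in the available text and cannot carry that reading. Section 16.1.2 assigns such an event to ADE.
- **The direction is cautious.** Merging can only raise the ADE count, and the study has no hypothesis test or ADE threshold to distort. This is true of the count. It does not cover the anticipated label, which makes an unexpected event look expected.
- **Narrowing the ADE definition would do harm.** Section 16.2 uses ADE as a trigger for 24-hour reporting and for the sponsor's medical review. A device-only definition would drop non-serious procedure-related events from both unless 16.2 were rewritten. This stands, and it determines the form of the fix.

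**Conclusion.** The point holds within limits. Followed as written, the ADE, SADE and ASADE incidences include procedure-only events, the device-relatedness row lacks a device-only definition, and an unexpected serious procedure-only event is classed as anticipated by default. These conclusions rest on the definitions alone and need no assumption about rates.

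The size is unknown. The 11.8% against 2% is an illustration under assumed, independent risks. The largest ratio in the table arises only from pairing the lowest assumed device rate with the highest assumed procedure rate. Neither should be read as a forecast of the study's results.

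What is at stake is the reading of one family of safety rows. The primary endpoint and the separately planned device-related results are unaffected. The point is still worth correcting, because in a single-arm study of anchor safety a clean device-only rate is a basic result, and the plan is one clarification short of producing it.

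**What to change.** Keep the ADE definition in 16.1.2 and the reporting and review triggers in 16.2 as they are. Then:

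1. Record relationship to the device and relationship to the procedure as two separate assessments for every adverse event, as 16.2 implies.
2. State in 14.4 and the SAP that the device-relatedness row uses the device assessment only.
3. Split the ADE and SADE rows into device-related (with or without relation to the procedure) and procedure-only. The two parts add up to the existing event totals; a subject with events of both kinds appears in both subject counts.
4. Reconcile the USADE and ASADE definitions in 16.1.4, so that a serious procedure-only event is not labelled anticipated merely because it fails the device requirement.

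The cost is small. Investigators make two attributions per event, the CRF may need one more field, and the table gains a few rows. Section 14 has the SAP finalised before database lock, so the analysis wording can be settled there. The separate attributions should be in place while charts are being reviewed, to avoid going back to the sites.
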